#### Analysis of the Pittsburgh Sleep Quality Index

Observed and change from Baseline values for the overall and component scores of the PSQI are to be summarised by descriptive statistics for the PAC1, PAC2 and PAC3 periods by treatment group.

The frequency (n) and percentage (%) of subjects in each category (good or poor) of PSQI Total Score is to be presented by treatment group for BAE, PAC1, PAC2 and PAC3.

A point estimate and exact 95% confidence interval for the difference in proportion of subjects that had a good response is to be calculated for each treatment group vs placebo using the following SAS code:

Document: TH005 SAP Version 2.docx

Author: [name]

Version Number:

2.0

Version Date:

24MAR2017

Template No: CS\_TP\_BS016 – Revision 3

Effective Date: 01May2012

Reference: CS\_WI\_BS005

Copyright © 2012 Quintiles Transnational Corp. All rights reserved.

The contents of this document are confidential and proprietary to Quintiles Transnational Corp. Unauthorized use, disclosure or reproduction is strictly prohibited.

---

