# 2.2 Secondary Objectives

The secondary objectives of the study are:

- To evaluate the safety and tolerability of HDM-SPIRE
- To evaluate the effect of HDM-SPIRE on rhinoconjunctivitis specific quality of life
- To evaluate the effect of HDM-SPIRE on sleep quality

VERSION FINAL 4.0 CONFIDENTIAL PAGE 20 OF 92

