#### 3.2.3 **Exploratory Endpoints**

- Rhinoconjunctivitis symptom scores measured using a visual analogue scale (VAS) during the BAE and each PAC period
- Mean CS in the HDM-SPIRE treatment groups compared with placebo during PAC1 and PAC2 periods.
- Mean TRSS in the HDM-SPIRE treatment groups compared with placebo during PAC1 and PAC2 periods.
- Mean RMS in the HDM-SPIRE treatment groups compared with placebo during PAC1 and PAC2 periods.
- Mean component scores of the TRSS (nasal and non-nasal) in the HDM-SPIRE treatment groups compared with placebo during the PAC1 and PAC2 periods.
- Overall RQLQ score in the HDM-SPIRE treatment groups compared with placebo at the end of the PAC1 and PAC2 periods.
- Sleep quality measured using the Pittsburgh Sleep Quality Index (PSQI) for the HDM-SPIRE treatment groups compared with placebo at the end of each PAC and PAC period.

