#### 7.5.3.3.8 Sleep

The overall and component scores of the PSQI at the end of the BAE and each PAC period will be summarised descriptively.

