### 2.2. SECONDARY OBJECTIVES

The secondary objectives are:

- To evaluate the safety and tolerability of HDM-SPIRE
- To evaluate the effect of HDM-SPIRE on rhinoconjunctivitis-specific quality of life using the rhinoconjunctivitis quality of life questionnaire (RQLQ)
- To evaluate the effect of HDM-SPIRE on sleep quality using the Pittsburgh Sleep Quality Index (PSQI)

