#### Analysis of Rhinoconjunctivitis Quality of Life Questionnaire

A point estimate and two-sided 95% confidence interval for the difference in adjusted means between the active treatment groups and placebo during the PAC1, PAC2 and PAC3 periods are to be calculated using an analysis of covariance (ANCOVA) with treatment, period and pooled region as main effects, gender, asthma status and Baseline RQLQ as covariate and a treatment by-period interaction for the Overall RQLQ score as well as each of the 7 domains individually.

- The treatment difference corresponding to the PAC3 period is to be utilised for the secondary analysis
- The treatment difference corresponding to the PAC1 and PAC2 periods are to be utilised as exploratory analyses

Observed and change from Baseline values are to be summarised by descriptive statistics for the PAC1, PAC2 and PAC3 periods by treatment group, for the Overall RQLQ score as well as each of the 7 domains individually.

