**EXACT OR RISKDIFF RELRISK(METHOD=SCORE);**

**RUN;****15.3.1.3. Asthma Control Test**

The Asthma Control Test (ACT) consists of 5 questions and is to be completed by all asthmatic subjects at the clinical Visits at the end of BAE, PAC1, PAC2 and PAC3. The questions are to be completed by the subjects stating how they have been over the last 4 weeks with regards the following:

- How much of the time did your asthma keep you from getting as much done at work, school or at home?
- How often have you had shortness of breath?
- How often did your asthma symptoms (wheezing, coughing, shortness of breath, chest tightness or pain) wake you up at night or earlier than usual in the morning?
- How often have you used your rescue inhaler or nebulizer medication?
- How would you rate your asthma control?

Each question has a 5 point scale (1 to 5) where 1 represents the least control and 5 represents optimal control. The ACT score is the mean of the 5 questions and therefore also between 1 (severely uncontrolled) and 5 (totally controlled).

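### Sleep quality by PSQI is a secondary objective, but its only between-arm comparison is an unadjusted good/poor split with no baseline term and no stated period

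*SAP*

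**What the plan says.** **Objective.** Protocol 2.2 lists among its secondary objectives: "To evaluate the effect of HDM-SPIRE on sleep quality". SAP 2.2 repeats this and names the PSQI. SAP 2.3 makes PSQI exploratory at the end of PAC1 and PAC2 only, which leaves PSQI at PAC3 to the secondary objective.

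**Endpoint tier.** Protocol 3.2.2 does not include PSQI among the secondary efficacy variables. Protocol 3.2.3 lists it as exploratory: "Sleep quality measured using the Pittsburgh Sleep Quality Index (PSQI) for the HDM-SPIRE treatment groups compared with placebo". SAP 15.3 also places it under other exploratory efficacy.

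**Analysis.** Protocol 7.5.3.3.8 plans description only: "The overall and component scores of the PSQI at the end of the BAE and each PAC period will be summarised descriptively". SAP 15.3.1.2 keeps the scores descriptive: "Observed and change from Baseline values for the overall and component scores of the PSQI are to be summarised by descriptive statistics". It tabulates good (total 5 or less) and poor (above 5) by arm at BAE and each PAC period. It then adds one comparison of each active arm with placebo: "A point estimate and exact 95% confidence interval for the difference in proportion of subjects that had a good response is to be calculated". The SAS code crosses treatment with outcome and has no baseline, covariate, stratum or period term. The odds ratio and relative risk it also requests come from the same unadjusted table.

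**Comparator.** RQLQ, the questionnaire for the other patient-reported secondary objective, gets an ANCOVA with "gender, asthma status and Baseline RQLQ as covariate" and a PAC3 contrast (SAP 15.2.1.6).

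**The concern.** The PSQI total is the sum of seven components scored 0-3, so it runs from 0 to 21. Cutting it at 5 turns it into a status at a visit. A subject who falls from 14 to 6 does not count as good. A subject at 4 before treatment and still at 5 or below afterwards does, although the SAP calls this a good response. No entry criterion in Protocol 4.2 or 4.3 requires poor sleep, so some subjects may be good sleepers at baseline.

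What is at stake is how precisely a stated secondary objective is answered. The comparison leaves out both the gradation in the score and the baseline value that would explain part of its variation. Because no period is named, an analyst could also run it at PAC1, PAC2 or PAC3 and still follow the text.

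**Working it through.** **1. The plan's own figure.** The documents give no sample size or power for PSQI. The primary calculation (Protocol 7.2, SAP 3.2: difference 0.32, SD 0.986, two-sided 5%, 80% power) reproduces: n = 2 × [0.986 × (1.960 + 0.842) / 0.32]² = 149.04, so 150 per arm. Only the 150 is carried forward.

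**2. Assumptions.** None of these is in the documents: proportion good on placebo p = 20-80%; a normal latent score; baseline to follow-up correlation r = 0.3-0.7.

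**3. Information kept by the split.** Relative to an unadjusted analysis of the total, it is φ(c)² / [p(1−p)], with c = Φ⁻¹(p).

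| p | φ(c) | Kept | Equivalent n out of 150 |
|---|---|---|---|
| 50% | 0.399 | 0.637 | 95 |
| 30% or 70% | 0.348 | 0.576 | 86 |
| 20% or 80% | 0.280 | 0.490 | 73 |

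The split alone therefore loses about 36-51%.

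**4. Adding the missing baseline adjustment.** Multiply by (1 − r²):
- r = 0.3: 45-58% kept
- r = 0.5: 37-48% kept
- r = 0.7: 25-33% kept

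The loss exceeds one half over the whole 20-80% range only when 0.637 × (1 − r²) < 0.5, that is, r above about 0.46.

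**5. Illustrative power, standardised difference 0.32 (assumed), 150 per arm, two-sided 5%.**
- Unadjusted total: SE = √(2/150) = 0.1155; 0.32/0.1155 = 2.77; power Φ(2.77 − 1.96) = 79%.
- Baseline-adjusted total: SE = √[(2/150)(1 − r²)]. At r = 0.4, SE = 0.1058 and power is 86%. At r = 0.6, SE = 0.0924 and power is 93%.
- Split: p₁ = Φ(c + 0.32), SE = √{[p(1−p) + p₁(1−p₁)]/150}. At p = 30%, p₁ = 41.9%, SE = 0.0550 and power is 58%. At p = 50%, p₁ = 62.6%, SE = 0.0568 and power is 60%. At 20% or 70% it is 53%, and at 80% it is 45%.

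**6. A check that does not fix the effect at 0.32.** Set the effect so that the adjusted total has exactly 80% power at 150 per arm. The split then has 45-60% at r = 0, 36-49% at r = 0.5 and 27-36% at r = 0.7 (p = 20-80%). The ordering does not depend on the chosen effect, and it holds even with no baseline correlation.

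**7. Chance baseline imbalance.** The 95% range for the difference between two arms in baseline proportion good is ±1.96 × √[2p(1−p)/150]. This is ±9.1 points at 20%, ±10.4 at 30% and ±11.3 at 50%.

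**The case against.** The best defence is that PSQI is an exploratory endpoint in a Phase II trial. Protocol 3.2.3, Protocol 7.5.3.3.8 and SAP 15.3 agree on that, and the SAP already does more than the descriptive summary the protocol promised. This stands as far as endpoint tier goes, and it limits how serious the point is. It does not remove it. The objective is secondary in both documents, SAP 2.3 calls only PAC1 and PAC2 PSQI exploratory, and Protocol 3.2.3 itself speaks of comparison with placebo. The tiers conflict, and the one comparison the SAP makes is an inefficient one.

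A reader might infer that baseline is ignored altogether. It is not: change from baseline is summarised by arm, and good/poor is tabulated at BAE. A move from 14 to 6 would appear there as −8. Baseline is missing only from the comparison.

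A reader might also infer that baseline imbalance biases the result. Randomisation protects against that. Chance imbalance enters the estimate only as far as baseline predicts outcome, so this is a matter of precision.

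The RQLQ sleep domain (three items) does get a baseline-adjusted PAC3 comparison under SAP 15.2.1.6. That gives partial cover, but it is not the instrument SAP 2.2 names for this objective.

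Finally, the SAP text asks for an estimate and interval and names no test for PSQI, so power is only an indirect measure. The information ratios in steps 3 and 4 of the working are the more direct one.

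**Conclusion.** The concern holds in this form: a secondary objective has no baseline-adjusted comparison of its own instrument's total score, the comparison it does have is an unadjusted split with no stated period, and the tier of PSQI is inconsistent within each document.

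On the stated assumptions the split alone costs about 36-51% of the information in the total. It is tempting to say that most of the information is discarded. That follows over the whole 20-80% range only when the missing baseline adjustment is counted and the correlation is about 0.46 or higher, and the documents give no correlation.

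The power figures are illustrations, not findings about this trial. In particular, the standardised difference of 0.32 should not be read as the Combined Score effect carried over: that calculation gives 0.32/0.986 = 0.325 on an SD that already allows for the baseline covariate, so applying (1 − r²) to it would count the adjustment twice. What holds without a particular effect or correlation is the direction: under the normal latent model, analysing the total is more precise than splitting it, and adjusting for a correlated baseline adds to that. The primary conclusion is untouched.

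**What to change.** In SAP 15.3.1.2:

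1. Add a baseline-adjusted analysis of the PSQI total. Use either the MMRM of SAP 15.1.3 with baseline PSQI in place of baseline CS, or an ANCOVA of the PAC3 total with the kind of covariates used for RQLQ. Either is adequate.
2. Name the PAC3 contrast of each active arm with placebo, with its 95% confidence interval, as the analysis for the sleep objective.
3. Keep the good/poor comparison as supportive, and state the period it uses.
4. Reconcile the tier of PSQI: the objectives (Protocol 2.2, SAP 2.2) against the endpoint and analysis sections (Protocol 3.2.3 and 7.5.3.3.8, SAP 15.3).

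The cost is one more run of a model already in the plan and a few lines of text. No new data are needed, because PSQI is collected at the end of BAE and of every PAC period.

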**PROC FREQ;**

**TABLES** treatment\*outcome / CMH;  
**EXACT OR RISKDIFF RELRISK(METHOD=SCORE);**

**RUN;****15.3.1.3. Asthma Control Test**

The Asthma Control Test (ACT) consists of 5 questions and is to be completed by all asthmatic subjects at the clinical Visits at the end of BAE, PAC1, PAC2 and PAC3. The questions are to be completed by the subjects stating how they have been over the last 4 weeks with regards the following:

- How much of the time did your asthma keep you from getting as much done at work, school or at home?
- How often have you had shortness of breath?
- How often did your asthma symptoms (wheezing, coughing, shortness of breath, chest tightness or pain) wake you up at night or earlier than usual in the morning?
- How often have you used your rescue inhaler or nebulizer medication?
- How would you rate your asthma control?

Each question has a 5 point scale (1 to 5) where 1 represents the least control and 5 represents optimal control. The ACT score is the mean of the 5 questions and therefore also between 1 (severely uncontrolled) and 5 (totally controlled).

**Analysis of the Asthma Control Test**

Observed and change from Baseline values for the ACT score is to be summarised by descriptive statistics for the PAC1, PAC2 and PAC3 periods by treatment group.

**15.3.1.4. Use of Concomitant Medications Associated with Rhinoconjunctivitis or Related Conditions**

Concomitant medication use associated with rhinoconjunctivitis or related conditions are to be analysed for the SAF population.

Medications associated with rhinoconjunctivitis or related conditions are defined as medications where the Concomitant Medications eCRF (CMDT) question 'Is the medication used for HDM allergy?' or 'Is the medication used for other allergy?' are indicated as 'Yes'. Concomitant medications are defined as in Section 12 Medications.

Subjects are to be categorised as either 'used' or 'not used' any concomitant medications associated with rhinoconjunctivitis or related conditions.

**Analysis of the Concomitant Medication Use**

The frequency (n) and percentage (%) of subjects in each category is to be presented per treatment group.

A point estimate and exact 95% confidence interval for the difference in proportion of subjects that used concomitant medication for rhinoconjunctivitis or related conditions is to be calculated for each treatment group

---

Document: TH005 SAP Version 2.docx  
Author: [name]

Version Number: 2.0  
Version Date: 24MAR2017

Template No: CS\_TP\_BS016 – Revision 3  
Effective Date: 01May2012

Reference: CS\_WI\_BS005

---

vs placebo using the following SAS code:

```
PROC FREQ;
  TABLES treatment*outcome / CMH;
  EXACT OR RISKDIFF RELRISK(METHOD=SCORE);
RUN;
```

#### 15.3.1.5. Home Environment Exposure and Control Measures

##### Control Measures

The frequency (n) and percentage (%) of subjects implementing the following control measures are to be presented for BAE, PAC1, PAC2 and PAC3 by treatment group, as captured on the House Dust Mite Control Measures eCRF (HDM1/2).

- Allergy-proof coverings for mattresses, pillows or quilts
- Sprays or chemicals to kill house dust mites
- Air filters
- Air management equipment
- Curtains

All additional information on control measures is to be listed only.

##### Home Environment Exposure

Subjects are to be issued with home dust collection kits on Consent Visit 1A and PAC3 Visit 4E.

House dust samples are to be collected following Consent Visit 1A and prior to the end of PAC3 Visit 4F/5. In the event that multiple samples are collected on different dates prior to Visit 4F/5 the last sample collected is to be analysed as the Visit 4F/5 sample.

Dust samples are to be tested for the following allergens and reported in mg/kg:

- Mite allergens der p 1
- Mite allergens der f 1
- Cat allergens fel d 1
- Dog allergens can f 1
- Mouse allergens mus m 1
- Rat allergens rat n 1
- Cockroach allergens bla g 2

---

Document: TH005 SAP Version 2.docx  
Author: [name]

Version Number: 2.0  
Version Date: 24MAR2017

Template No: CS\_TP\_BS016 – Revision 3  
Effective Date: 01May2012

Reference: CS\_WI\_BS005

Copyright © 2012 Quintiles Transnational Corp. All rights reserved.  
The contents of this document are confidential and proprietary to Quintiles Transnational Corp. Unauthorized use, disclosure or reproduction is strictly prohibited.

---

- Alternaria allergens alt a 1

Observed and change from Baseline values for each allergen is to be summarised by descriptive statistics for Baseline and Visit 4F/5 by treatment group.

Assessments reported as “< X”, i.e. below the lower limit of quantification (BLQ), or “> X”, i.e. above the upper limit of quantification (ULQ), are to be converted to X for the purpose of quantitative summaries, but are to be presented as recorded, i.e. as “< X” or “> X” in the listings.

All allergens identified as entered on the Issue dust Collection Pack eCRF (DMKIT) is to be listed.

## 16. SAFETY OUTCOMES

All outputs for safety outcomes are to be based on the SAF population.

There is to be no statistical comparisons between the treatment groups for safety data, unless otherwise specified within the relevant section.

### 16.1. ADVERSE EVENTS

An AE is defined as any untoward medical occurrence in a subject administered study treatment that does not necessarily have a causal relationship with the treatment. An AE can therefore be any unfavourable and unintended sign (i.e. an abnormal laboratory finding), symptom (i.e., rash, pain, discomfort, fever, dizziness, etc.), disease (i.e., peritonitis, bacteraemia, etc.) or outcome of death temporally associated with the use of study treatment, whether or not considered causally related to the study medication.

Adverse Events (AEs) are to be coded using MedDRA Version 19.0.

Adverse events are to be classified as either pre-treatment AEs or treatment-emergent adverse events (TEAEs) based on the start date of the event as follows:

- Pre-treatment AEs: Defined as any AE which started or worsened on or after informed consent and before study medication administration
- TEAE: Defined as any AE which started or worsened on or after first study medication administration.

See Appendix 2 for handling of partial dates for AEs. In the case where it is not possible to define an AE as treatment-emergent or not, the AE is to be classified as the worst case; i.e. treatment-emergent.

An overview of the frequency (n) and percentage (%) of subjects is to be provided for the following TEAEs together with the actual number of mentions (m) of the event per category:

- Any TEAE
- Serious TEAEs
- TEAEs leading to death

---

Document: TH005 SAP Version 2.docx

Author: [name]

Version Number:

2.0

Version Date:

24MAR2017

Template No: CS\_TP\_BS016 – Revision 3

Effective Date: 01May2012

Reference: CS\_WI\_BS005

Copyright © 2012 Quintiles Transnational Corp. All rights reserved.

The contents of this document are confidential and proprietary to Quintiles Transnational Corp. Unauthorized use, disclosure or reproduction is strictly prohibited.

---

- Life-threatening TEAEs
- TEAEs leading to premature study and treatment discontinuation
- Treatment related TEAEs leading to premature treatment discontinuation
- Severe TEAEs
- TEAEs related to study medication
- TEAEs of special interest
- TEAEs within 24 hours of any dose of study medication

In addition to the overview of TEAEs, incidence of all TEAEs in the sub-sections below is to be presented by System Organ Class (SOC) and Preferred Term (PT). If an AE occurs more than once the subject is to be counted once per SOC and PT as relevant.

### **16.1.1. ALL TEAEs**

#### **16.1.1.1. Severity**

Severity is classed as mild/moderate/severe (increasing severity). TEAEs with a missing severity are to be classified as severe. If a subject reports a TEAE more than once within that SOC/PT, the AE with the worst case severity is to be used in the corresponding severity summaries.

#### **16.1.1.2. Relationship to Study Medication**

Relationship, as indicated by the Investigator, is classed as 'Not related', 'Unlikely to be related' or 'Related' (increasing severity of relationship). TEAEs with a missing relationship to study medication are to be regarded as 'Related' to study medication. If a subject reports the same AE more than once within that SOC/ PT, the AE with the worst case relationship to the study medication is to be used in the corresponding relationship summaries.

### **16.1.2. SERIOUS TEAEs**

Serious TEAEs are those events recorded as 'Serious' on the Adverse Events Details eCRF (AEDT).

### **16.1.3. TEAEs LEADING TO DEATH**

Treatment-emergent AEs leading to Death are those events for which the Outcome is recorded as 'Death' or the reason for seriousness of the event is indicated as 'Death' on the Adverse Events Details eCRF (AEDT).

---

Document: TH005 SAP Version 2.docx  
Author: [name]

Version Number: 2.0  
Version Date: 24MAR2017

Template No: CS\_TP\_BS016 – Revision 3  
Effective Date: 01May2012

Reference: CS\_WI\_BS005

Copyright © 2012 Quintiles Transnational Corp. All rights reserved.  
The contents of this document are confidential and proprietary to Quintiles Transnational Corp. Unauthorized use, disclosure or reproduction is strictly prohibited.

---

**16.1.4. LIFE-THREATENING TEAES**

Life-threatening TEAES are those events where the reason for seriousness of the event is specified as "Life-threatening" on the Adverse Events Details eCRF (AEDT).

**16.1.5. TEAES LEADING TO PREMATURE STUDY OR TREATMENT DISCONTINUATION**

Treatment-emergent AEs leading to premature study discontinuation are to be identified as TEAES where the Outcome on the Adverse Events Detail eCRF (AEDT) is indicated as "Subject withdrawn because of this event".

**16.1.6. TREATMENT RELATED TEAES LEADING TO PREMATURE TREATMENT DISCONTINUATION**

Treatment related TEAES leading to premature treatment discontinuation are to be identified as TEAES where the Outcome on the Adverse Events Detail eCRF (AEDT) is indicated as "Subject withdrawn because of this event" and the Causality is indicated as "Related" and the primary reason for treatment termination on the End of Treatment eCRF (EOT) is indicated "Adverse Event".

